#### 3.5 COST AND COMPENSATION

### 3.5.1 Costs

NIH does not bill health insurance companies or participants for any research or related clinical care that participants receive at the NIH Clinical Center. If some tests and procedures performed outside the NIH Clinical Center, participants may have to pay for these costs if they are not covered by insurance company. Medicines that are not part of the study treatment will not be provided or paid for by the NIH Clinical Center.

### 3.5.2 Compensation

Participants will not be compensated on this study.

### 3.5.3 Reimbursement

The NCI will cover the costs of some expenses associated with protocol participation. Some of these costs may be paid directly by the NIH and some may be reimbursed to the participant/guardian as appropriate. The amount and form of these payments are determined by the NCI Travel and Lodging Reimbursement Policy.

### 3.6 CRITERIA FOR REMOVAL FROM PROTOCOL THERAPY AND OFF STUDY CRITERIA

Prior to removal from study, effort must be made to have all subjects complete an end of treatment visit approximately 30 days after the last dose of study therapy.

# 3.6.1 Criteria for removal from protocol therapy

- Progressive disease
- Participant requests to be withdrawn from active therapy
- Unacceptable toxicity as defined in Section 3.3
- Toxicity related dose delay lasting longer than 28 days in which case participant will be removed from the drug causing the toxicity
- Investigator discretion
- Requirement for any drug deemed to cause an significant drug-drug interaction that could impact the study treatment (at discretion of the PI and/or Associate Investigator and as discussed in Section 4.1)

#### 3.6.2 Off-Study Criteria

- Participant requests to be withdrawn from study
- Death
- PI decision to end the study
- Participant lost to follow up

• Investigator's discretion

# 3.6.3 Lost to Follow-up

A participant will be considered lost to follow-up if he or she fails to return for 3 consecutive scheduled visits and is unable to be contacted by the study site staff.

The following actions must be taken if a participant fails to return to the clinic for a required study visit:

- The site will attempt to contact the participant and reschedule the missed visit over the course of the 3 consecuteively mised visits and counsel the participant on the importance of maintaining the assigned visit schedule and ascertain if the participant wishes to and/or should continue in the study.
- Before a participant is deemed lost to follow-up, the investigator or designee will make every effort to regain contact with the participant (where possible, 3 telephone calls and, if necessary, a certified letter to the participant's last known mailing address or local equivalent methods). These contact attempts should be documented in the participant's medical record or study file.
- Should the participant continue to be unreachable, he or she will be considered to have withdrawn from the study with a primary reason of lost to follow-up.

# 4 CONCOMITANT MEDICATIONS/MEASURES

Participants will be on concomitant androgen suppression therapy with a GnRH agonist or GnRH antagonist (unless they have had a prior orchiectomy). Participants may also be on concomitant drugs to prevent bone loss, including bisphosphonates and denosumab.

Other supportive care with blood components, antibiotics, analgesics, general medical therapy, etc., will be delivered as required. Use caution when co-administering medication which may lower the seizure threshold.

# 4.1 GENERAL GUIDELINES

All medications (other than study drug) and significant non-drug therapies (including physical therapy and blood transfusions) taken within 28 days of starting study treatment through the 30 day end of treatment visit should be reported on the CRF.

While participants on protocol treatment, all medications required for the health of the participant are allowed with the following exceptions:

- Concurrent chemotherapy or secondary hormonal treatment outside of the investigational treatment
- Concurrent cancer immunotherapy (e.g. therapeutic cancer vaccines)
- Concurrent anti-cancer radionuclides

Concomitant use of herbal supplements should be discouraged and/or avoided.

Palliative radiotherapy is allowed for pre-existing small areas of painful metastases (e.g. bone) that are uncontrolled with local or systemic analgesics as long as no evidence of disease progression is present and the metastatic site treated is not a target lesion.

- 4.1.1 Seizure threshold lowering drugs
  - Use caution when co-administering medications which may lower the seizure threshold (e.g. atypical antipsychotic drugs, phenothiazines, bupropion, aminophylline/theophylline, tricyclic and tetracyclic antidepressants, lithium, pimozide, venlafaxine).
- 4.1.2 Cytochrome P450 and P-glycoprotein
  - Co-administration of enzalutamide with strong or moderate CYP2C8 inducers (e.g., rifampin) may alter the plasma exposure of enzalutamide. Moderate CYP2C8 inducers maybe used concomitantly with enzalutamide at the Principal Investigator or designee's discretion. If co-administration of enzalutamide with a strong CYP2C8 inhibitor cannot be avoided, reduce the dose of enzalutamide to 80 mg per day.
  - Co-administration of enzalutamide with strong CYP3A4 inducers (e.g., carbamazepine, phenobarbital, phenytoin, rifabutin, rifampin, rifapentine) may decrease the plasma exposure of enzalutamide and should be avoided if possible. Selection of a concomitant medication with no or minimal CYP3A4 induction potential is recommended.
  - Moderate CYP3A4 inducers (e.g., bosentan, efavirenz, etravirine, modafinil, nafcillin) and St. John's Wort may also reduce the plasma exposure of enzalutamide and should be avoided if possible.
  - Concomitant use of enzalutamide with narrow therapeutic index drugs that are metabolized by CYP3A4 (e.g., alfentanil, cyclosporine, dihydroergotamine, ergotamine, fentanyl, pimozide, quinidine, sirolimus and tacrolimus), CYP2C9 (e.g., phenytoin, warfarin) should be avoided, as enzalutamide may decrease their exposure.
  - Grapefruit, Seville oranges, and starfruit affect P450 and PgP activity. Concomitant use should be avoided.

# 4.2 SUPPORTIVE CARE

Participant should receive general concomitant and supportive care medications based on best medical practice.

The use of any natural/herbal products or other "folk remedies" should be discouraged.

The preferred anticoagulant therapy is subcutaneous heparin or low molecular weight heparin. A participant may continue warfarin (with increased INR monitoring) or other anticoagulant agents under close supervision and at the discretion of the Principal Investigator or designee.

#### 4.2.1 Concomitant medications

All medications (prescriptions or over-the-counter medications) continued at the start of the trial or started during the study or until 30 days from the end of the last protocol treatment and different from the study medication must be documented.

4.2.2 Palliative radiotherapy

Palliative radiotherapy may be used for the treatment of pain at the site of bony metastases that were present at baseline, provided the Principal Investigator or designee does not feel that these are indicative of clinical disease progression during the study period.

CRLX101 should be discontinued for a minimum of 3 days before the participant undergoes palliative radiation treatment. CRLX101 should be restarted at least 14 days but no more than 21 days after palliative radiation, as long as any bone marrow toxicity has recovered  $\leq$  Grade 1.

Consistent with the PREVAIL trial which demonstrated improved survival in mCRPC and led to FDA approval in the chemotherapy-naïve subgroup, palliative radiation is allowed to be given in combination with enzalutamide.

4.2.3 Administration of other anti-cancer agents

Participants must not receive any other concurrent anti-cancer therapy, including investigational agents, while on study treatment. Participants may continue the use of bisphosphonates for bone disease provided the dose is stable before and during the study.

4.2.4 Medications that may NOT be administered

No other chemotherapy, immunotherapy, hormonal therapy (with the exception of LHRH agonists/antagonists that will be continued while on study) or other novel agent is to be permitted while the participant is receiving study medication.

Live virus and bacterial vaccines should not be administered whilst the participant is receiving CRLX101 and during the 30-day follow-up period. An increased risk of infection by the administration of live virus and bacterial vaccines has been observed with conventional chemotherapy drugs.

# **5 BIOSPECIMEN COLLECTION**

# 5.1 CORRELATIVE STUDIES FOR RESEARCH/PHARMACOKINETIC STUDIES

Pharmacokinetic analyses of camptothecin will assessed at two points during the study treatment. Plasma camptothecin concentrations will be measured before and after initiation of enzalutamide treatment to determine the impact of enzalutamide on CRLX101/camptothecin pharmacokinetics. Urine camptothecin concentrations will also be measured with and without the co-administration of sodium bicarbonate to assess the impact of urine alkalinization on the physicochemical characteristics of camptothecin accumulating in the bladder.

Multiple pharmacodynamic biomarkers will be assessed prior to study treatment and at multiple time points following treatment. The inhibition of HIF-1 $\alpha$  will be measured indirectly via the circulating plasma protein biomarker, VEGF, a prominent downstream target and marker of tumor angiogenesis. The presence of acquired resistance will be assessed via the enumeration of CTCs and the measurement of androgen receptor splice variation in CTCs. The presence of CTCs with high phenotypic genomic instability will also be measured before and after initiation of combination therapy.

Biomarkers of DNA damage will be measured using a novel NanoString platform aimed to measure gene expression of 192 gene markers. Evaluation of the response to a DNA damaging agent (camptothecin) may help generate hypotheses for future studies.

Table 7: Correlative Stud	ies Summary
---------------------------	-------------

Sample	Assay	Time Points	Type of Tube/ Sample (sample amount)	Location of specimen analysis
Plasma	Pharmacokinetics	Refer to PK sampling outlined in Section 5.1.1	Refer to PK sampling outlined in Section 5.1.1	[name] Lab
Urine	Pharmacokinetics	Refer to PK sampling outlined in Section 5.1.1	Refer to PK sampling outlined in Section 5.1.1	[name] Lab
Whole Blood	Circulating Plasma Proteins (VEGF)	Pre-treatment on C1D1, C2D15, C6D1, and at disease progression	Purple top EDTA (one 6 mL each)	[name] Lab
	Nanostring DNA damage response panel (192 genes)	Pre-treatment on C1D1, C2D15, and at disease progression	PAXgene RNA (one 2.5 mL each)	[name] Lab
Circulating Tumor Cells (CTCs) and AR Analysis	Enumeration Androgen Receptor (AR) Analysis Genomic Instability γ-H2AX Expression (if feasible)	Pre-treatment on C1D1, C2D15, C6D1and at disease progression	one 10 mL Streck Cell-Free DNA and one 2.5 mL PAXgene RNA	EPIC Sciences and [name] Lab

# 5.1.1 Pharmacokinetics

Table 8: Plasma Pharmacokinetic Sample Collection with CRLX101 Infusion. Note: Samples are to be approximately drawn around these time points, with the collection times noted on the tubes.

Sample	Cycle	Day	PK Collection with CRLX101 Infusion
1	1	1	Predose

Sample	Cycle	Day	PK Collection with CRLX101 Infusion
2	1	1	Mid-infusion (~30 minutes into infusion)
3	1	1	End of Infusion (EOI)
4	1	1	1 hr post EOI
5	1	1	2 hr post EOI
6	1	1	3 hr post EOI
7	1	1	4 hr post EOI
8	1	1	8 hr post EOI
9	1	1	12 hr post EOI
10	1	2	24 hr post EOI
11	2	15	Predose
12	2	15	Mid-infusion (~30 minutes into infusion)
13	2	15	End of infusion (EOI)
14	2	15	1 hr post EOI
15	2	15	2 hr post EOI
16	2	15	3 hr post EOI
17	2	15	4 hr post EOI
18	2	15	8 hr post EOI
19	2	15	12 hr post EOI
20	2	16	24 hr post EOI

# 5.1.1.1 Plasma PK

# CRLX101 Pharmacokinetics

To identify a drug-drug interaction between CRLX101, camptothecin, and enzalutamide on clinically-relevant doses, blood samples for the determination of camptothecin plasma concentrations will be obtained from each participant on cycle 1 day 1 prior to CRLX101 administration, when CRLX101 will be administered alone. Blood will be collected into a 6 mL

sodium heparin tube (BD, Franklin Lakes, NJ) at the following time points: pre-infusion, midinfusion, immediately at end of infusion (EOI), then 1, 2, 3 4, 8, 12, and 24 hr post-EOI. After the 24 hour time point, the first dose of enzalutamide will be administered.

On cycle 2 day 15 (C2D15), after being on the daily combination of CRLX101 and enzalutamide for at least 4 weeks to establish steady state, participants will have blood drawn at pre-infusion, mid-infusion, EOI, then 1, 2, 3, 4, 8, 12, and 24 hr post EOI. Comparisons of CRLX101 and camptothecin exposure between cycle 2 (with enzalutamide) and first-dose (alone) will determine the extent of a drug-drug interaction (if any) with enzalutamide.

Note: PK samples should be drawn approximately around the specified time points, with the collection times noted on the tubes.

# Enzalutamide Pharmacokinetics

Blood will be collected during the visit on C2D15 prior to the participant's scheduled dose of enzalutamide and the infusion of CRLX101 to measure enzalutamide trough plasma concentrations. Blood will be collected into a 6 mL sodium heparin tube (BD, Franklin Lakes, NJ). Enzalutamide steady-state trough concentrations during cycle 2 dosing will be compared to relevant literature to determine the extent of a drug-drug interaction with CRLX101 and camptothecin.

# Bioanalytical Measurements and Assay Methodology

Bioanalytical measurements of unconjugated camptothecin, conjugated camptothecin (measured indirectly), enzalutamide, and enzalutamide metabolites (e.g. N-desmethyl enzalutamide) will be conducted on an ultra HPLC-MSMS system using an assay developed and validated by the Clinical Pharmacology Program.

The PK sampling will also be used to monitor camptothecin and enzalutamide exposure metrics in order to correlate to pharmacodynamic endpoints, clinical response, toxicity, and pharmacogenetic analyses.

# 5.1.1.2 Urinary Clearance of CRLX101/camptothecin

To identify a mechanism of camptothecin-induced cystitis on clinically relevant doses, urine samples for the determination of camptothecin species (e.g. closed lactone vs. open carboxylate form) and nanoparticle concentrations will be obtained from each participant on C1D1 and C2D15, with or without the administration of sodium bicarbonate to alkalinize urine accumulating in the bladder.

Urine samples (dependent upon whether the participant needs to void) will be collected when feasible in willing participants at the discretion of the Principal Investigator from pre-infusion through 24 hours post-EOI. The nursing staff will be supplied with urine collection tubes for the duration of urine PK collection time frame. Each time the participant needs to void, the participant will be asked to notify the nurse, who will collect a urine sample, if feasible, and then record the date/time on each collection tube. Each collected sample will be kept separately and should be obtained using the "clean catch" method (total urinary excretion is not of importance).

On C1D1, participants will receive IV fluids pre- and post-infusion following the currently established hydration protocol (HP) for CRLX101. On C2D15, participants will follow the hydration protocol with the additional administration of oral sodium bicarbonate (HP+SB).

Comparisons of CRLX101 and camptothecin urinary accumulation between the HP and HP+SB protocols will be used to help characterize an underlying mechanism of cystitis and determine a potential method of prophylaxis for participants at high risk for camptothecin-induced cystitis.

Prior to C2D15, participants will be given instructions on how to administer sodium bicarbonate before their scheduled clinic appointment visit. **Table 9** provides recommendations for the administration of oral sodium bicarbonate on C2D15. The oral sodium bicarbonate dosing schedule may be modified at the discretion of the Principal Investigator or designee.

Timing	Dose, route, and frequency	
Starting from 48 hours prior to CRLX101 infusion	Take sodium bicarbonate by mouth, 650mg x2, 4 times a day (QID), for two days before CRLX101 infusion	
On the day of CRLX101 infusion	Take sodium bicarbonate by mouth, 650mg x2, 4 times a day (QID), for one day	
*Within Two Hours Prior to CRLX101 Infusion	If feasible, Obtain a Urine Sample for Analysis	
After CRLX101 infusion	Take sodium bicarbonate by mouth, 650mg x2, 4 times a day (QID), for one day after CRLX101 infusion	

Table 9: Recommended Urine Alkalinization Procedure On C2D15

**Note:** Doses may be reduced based on age (e.g. over 60) or based on renal function at the discretion of the Investigator. Dosing frequency, dose strength and dosing schedule may also be modified at the discretion of the Principal Investigator or designee. In the case of poor compliance to oral sodium bicarbonate administration for the experimental procedure, collection of urine samples will be done when feasible in willing participants, at the discretion of the principal investigator or designee

Urine collection will not be a requirement in participants with incontinence, conditions preventing urine collection by standard techniques, or other conditions at the discretion of the Principal Investigator or designee. If a participant with incontinence is willing to participate, a sterile catheter inserted into the bladder will be placed on C1D1 and C2D15 to facilitate urine collection.

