### 1.2.5.9 Camptothecin-Induced Cystitis

Cystitis is a common adverse event following CRLX101 administration. The proposed mechanism of toxicity involves the reclosing of the camptothecin lactone ring once the drug is cleared into the more acidic pH of the bladder. The closed lactone ring leads to reactivation of camptothecin, thus increasing the likelihood for off-target effect and subsequent toxicity in the bladder. The current management of the risk for cystitis involves dilution of the urine via increased hydration. Alkalinization of the urine is another proposed method of prophylaxis, which could be achieved via sodium bicarbonate administration. Although higher urine pH will limit the concentration of active camptothecin, it could lead to higher release of CPT from intact CRLX101 nanoparticles that are cleared renally. The use of sodium bicarbonate to circumvent high grade camptothecin-induced cystitis requires further investigation.

*In vitro* experiments were conducted at varying pH levels in urine following a 72-hour incubation at 37°C to measure the release of CPT from the CRLX101 nanoparticle and the ratio of lactone to carboxylate of the unconjugated CPT. While increasing pH lead to an increased rate of CPT release, the ratio of CPT species favored the carboxylate form, especially at pH values of 8 or greater (See Figure 5). Despite a higher concentration of total CPT, urine alkalinization led to a decrease in the active lactone form compared to lower urine pH values.

[figure not shown]

Figure 5: Total concentration of free CPT released from CRLX101 at various pH values (left) and the percentage of carboxylate form graphed against percentage of lactone form at various pH values (right).

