3.2.1.1 Hydration and Premedication Prior to CRLX101 Treatment

Subjects will receive IV hydration infused approximately over two hours with up to 1,000 mL of 0.9% sodium chloride solution before and after the administration of CRLX101 to reduce risk of cystitis adverse reaction. The administration rate and volume should follow standard site procedures and may be adjusted by the Principal Investigator or designee based on patient-specific factors. Participants should be encouraged to adequately hydrate throughout the cycle, especially during the first 48 hours following the infusion of CRLX101.

Subjects should be pre-medicated with the following drug classes 30-90 minutes prior to start of CRLX101 infusion to reduce likelihood of hypersensitivity adverse reactions:

- a corticosteroid (dexamethasone 20 mg IV or PO)
- an antihistamine (diphenhydramine 50 mg IV or PO)
- an H2 antagonist (famotidine 20 mg IV or PO; 30-60 minutes prior to start of CRLX101)
- an anti-emetic, (e.g., a 5-HT3 receptor antagonist)

At the discretion of the Principal Investigator or designee, a 650 mg dose of Acetaminophen PO may also be given.

The drug recommendations can be adjusted per local institutional guidelines with approval from the Principal Investigator or designee.

The example medications, route of administration, and dose indicated should be the medication-of-choice if clinically feasible. It is acknowledged that the premedication regimen may be altered for participant safety during the study (for example, if a participant experiences a hypersensitivity/infusion reaction related to study drug, the premedication regimen may be altered for subsequent cycle dosing based on the Principal Investigator or designee's discretion).

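### Urinary CRLX101 and camptothecin concentrations are compared between the hydration and hydration-plus-bicarbonate visits without any measure of urine dilution, so a difference in concentration cannot be attributed to bicarbonate

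*Combined protocol and SAP*

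**What the plan says.** Section 5.1.1.2 takes urine on C1D1 and C2D15 for "determination of camptothecin species (e.g. closed lactone vs. open carboxylate form) and nanoparticle concentrations". Samples "will be collected when feasible in willing participants at the discretion of the Principal Investigator from pre-infusion through 24 hours post-EOI". They are clean-catch aliquots kept separately. For each one the nurse is to "record the date/time on each collection tube", and the section adds that "total urinary excretion is not of importance". The analysis is stated as follows: "Comparisons of CRLX101 and camptothecin urinary accumulation between the HP and HP+SB protocols will be used to help characterize an underlying mechanism" of cystitis, and to identify a possible prophylaxis for participants at high risk. The bioanalytical paragraph of the same section lists accumulation, the ratio of lactone to carboxylate, and release of camptothecin from the nanoparticle. It does not rank them.

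On hydration, section 3.2.1.1 sets a ceiling of 1,000 mL of saline before and after the infusion, not a fixed volume. It continues: "The administration rate and volume should follow standard site procedures and may be adjusted by the Principal Investigator or designee based on patient-specific factors". Oral fluids are encouraged but neither fixed nor recorded. Section 1.2.5.9 explains why dilution matters here: "The current management of the risk for cystitis involves dilution of the urine via increased hydration".

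Section 5.4.1 mixes the stored urine with an equal volume of methanol. Section 10.4.7 makes the analysis descriptive and includes no dilution adjustment.

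**The concern.** A spot concentration is an amount divided by a volume. With only concentration and clock time, neither clearance nor the amount excreted can be computed, although the section is titled for the first and compares accumulation. If a participant's urine is more dilute at one visit than at the other, every concentration moves in the same proportion, whatever bicarbonate does.

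The unmeasured factor is the existing preventive measure itself. The comparison is meant to show what alkalinization adds to hydration, and for absolute concentrations it cannot separate the two.

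The error can run in either direction. In the in vitro work of section 1.2.5.9, higher pH released more camptothecin in total while lowering the active lactone form. More dilution on C2D15 would work against the expected rise in total free camptothecin and would enlarge a fall in lactone concentration. Less dilution on C2D15 would do the reverse. Section 5.1.1.2 also plans to correlate bladder exposure with toxicity and response, so the same concentrations are used a second time.

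**Working it through.** The plan states no effect size, standard deviation, sample size or power for the urine comparison, so there is no figure of its own to reproduce. The check has two parts.

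**1. Is dilution measured anywhere?**
- Section 5.1.1.2 records date and time for each tube. No volume is mentioned.
- Section 5.2.1 asks for date and exact time on the tube and on a PK sheet. The contents of that sheet are not shown.
- Section 5.4.1 describes aliquoting, methanol and freezing, with no creatinine, specific gravity or osmolality step.
- Table 6 (section 3.4) appears to place a urinalysis on C1D1 and C2D15. Its components are not listed, it is not per void, and it is not linked to the PK samples. The creatinine in the table's footnotes belongs to the acute care panel.

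**2. How much can volume alone move the readouts?**

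Inputs from the documents: 48-hour urinary excretion of 16.2% of dose as conjugated and 4.4% as unconjugated camptothecin (section 1.2.5.3), and a dose of 12 mg/m² (the lead-in dose at both urine visits, section 3.1.1). Assumptions: body surface area 1.9 m², the daily urine volumes below, and excretion identical at both visits.

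- Dose: 12 × 1.9 = 22.8 mg.
- Unconjugated over 48 h: 0.044 × 22.8 = 1.003 mg. Conjugated: 0.162 × 22.8 = 3.694 mg.
- Mean concentration = amount / (2 × daily volume).

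| Assumed volume, L/day | Unconjugated, mg/L | Conjugated, mg/L | Unconjugated / total |
|---|---|---|---|
| 2 | 0.251 | 0.923 | 0.214 |
| 3 | 0.167 | 0.616 | 0.214 |
| 4 | 0.125 | 0.462 | 0.214 |

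Dose, body surface area and excreted fraction cancel in the between-visit ratio:

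C(C2D15) / C(C1D1) = V(C1D1) / V(C2D15)

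- 2/3 = 0.67, a fall of 33%. 2/4 = 0.50, a fall of 50%. The reverse order, 3/2 = 1.5, is a rise of 50%.
- For an assumed base output of 1.0 to 2.0 L plus 0.5 to 2 L extra at one visit, the ratio runs from 2.0/2.5 = 0.80 down to 1.0/3.0 = 0.33.
- Masking: a true 1.5-fold rise in free camptothecin excreted, met by 3 L instead of 2 L, gives 1.5 × 2/3 = 1.0, which would read as no change.
- Within-sample fractions: 4.4 / (4.4 + 16.2) = 0.214 at every volume. The lactone-to-carboxylate ratio is unchanged for the same reason, since volume divides out of numerator and denominator.

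**The case against.** The strongest reply is that the readouts carrying the hypothesis do not depend on dilution. Section 1.2.5.9 places the mechanism in pH-driven closure of the lactone ring, section 5.1 states the aim as the effect of alkalinization on physicochemical characteristics, and both the lactone ratio and release from the nanoparticle are planned. This stands. A reader might infer that the whole comparison of the two visits is confounded by dilution. The documents do not support that: only the absolute concentrations are exposed.

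A second reply is that the bladder wall meets a concentration, not a total amount, so the remark on total excretion may be a deliberate choice of exposure measure. This also stands for describing exposure. It does not license attributing a between-visit difference in concentration to bicarbonate.

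Third, the same hydration protocol applies on both days within each participant, and adjustment for patient-specific factors would often apply at both. This is fair. A reader might suppose that water taken with the bicarbonate tablets makes C2D15 systematically more dilute, so that a fall in camptothecin would pass for a bicarbonate effect. No section mentions such water, and for total free camptothecin the protocol's own in vitro data point to a rise, which extra fluid would mask and not mimic. What remains is an unmeasured difference of unknown direction.

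Finally, correcting for dilution does not isolate bicarbonate. C1D1 is always the first dose and C2D15 the fourth, and study enzalutamide starts on C1D2. That is true and should be stated in the plan. Dilution is simply the easiest of these confounders to remove.

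**Conclusion.** The point holds for absolute urinary CRLX101 and camptothecin concentrations. As planned, a difference between C1D1 and C2D15 cannot be divided between dilution and alkalinization. It could mask the expected rise in total free camptothecin, or exaggerate or hide a fall in lactone concentration.

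The size follows from one-over-volume scaling: 33% lower for 3 L against 2 L, and 50% lower for 4 L against 2 L. The volumes are assumptions, because the documents give no urine output and no expected difference between visits. The absence of a dilution measure is read from the documents' silence, and the PK sheet and urinalysis components are not shown.

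The lactone-to-carboxylate ratio and the unconjugated share of total camptothecin are not affected. A reader might also infer that total excretion should be measured and summed. Voids collected only if feasible would not give a sound total, so the documents do not support that step. The objective is exploratory (sections 1.1.3.2 and 10.4.7), and no dosing, stopping or efficacy conclusion depends on it. Severity is minor.

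**What to change.** In section 5.1.1.2, with a matching line in section 10.4.7:

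- Name the lactone-to-carboxylate ratio and the unconjugated/total fraction as the main readouts for the comparison of the two visits.
- Assay creatinine on an aliquot of each urine PK sample taken before methanol is added, or with an assay checked in the methanol mixture. Record the IV fluid volume actually given on both days.
- Report creatinine-normalised total and unconjugated camptothecin beside the raw concentrations, stating the assumption of steady creatinine excretion.
- Describe raw concentration as bladder exposure that reflects dilution and alkalinization together.
- State that visit order and enzalutamide remain confounded with bicarbonate.

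The cost is one inexpensive assay per sample and one recorded volume per visit, with no new visit or void. Creatinine is preferable to void volume, because measuring volume would require capturing the whole void, which clean-catch sampling into tubes does not do.
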